1.2.1 Symptomatic treatment initiation

The main ICE affecting the interpretation of measurements will be initiation of ST.

MDS-UPDRS

Initiation of ST will be considered to impact the definition of the intervention effect of interest when measured using MDS-UPDRS Part I-III sum score as well as using MDS-UPDRS Part II and Part III subscales. Only Levodopa and Dopamine-agonist STs will be considered as having an impact on MDS-UPDRS, see [Section 5.3.3.3](#) for the classification of ST types and [Table 1-2](#) for how to handle other types of ST.

In the primary estimand analysis, the post-ICE data will be censored ('Hypothetical' strategy, assuming data is missing at random) and the data will be analyzed using a likelihood-based method of analysis, ie, a LMEM for longitudinal data/repeated measures with its implicit imputation approach (White, 2012) applied to all participants in the target population. This type of analysis will be referred to as 'in the absence of ST initiation'.

An alternative 'Hypothetical' handling strategy of this ICE will also be implemented as a supplementary estimand where data recorded under ST will be corrected using a de-mediation approach (see [Section 5.3.2.1.4](#)).

In a supplementary analysis to the primary estimand, the post-ICE data up to Month 18 will be included in the analysis ('Treatment policy' strategy) irrespective of whether the participant complied with the 12-hour ST washout: for all scheduled visits, study participants who start to receive ST over the study observation period will be asked to refrain from taking ST for at least 12 hours before the clinic visit and to bring the medication to the site. Visits where the participant did not comply with the 12-hour ST washout will be identified in the analysis datasets, but will not be censored from the analyses. If it is not possible to determine whether a participant completed the washout period for a particular visit, it will be assumed that they were compliant.

DaT-SPECT

A secondary endpoint will be the mean striatal dopamine receptor-specific binding ratio (SBR) as measured by DaT-SPECT. In this study, it will be assumed that DaT-SPECT signal is not affected by initiation or dose of levodopa (reviewed in Ikeda et al, 2019). Initiation of levodopa, dopamine agonists, and COMT inhibitors as well as change in dose or type will be considered NOT to impact the effect of interest for DaT-SPECT, and the post ICE data will be included in the main estimand analysis 'regardless of ST initiation' ("Treatment policy" strategy). Missing data due to scan not having taken place at the participant's or investigator's discretion will be treated as missing at random.

MAO-B inhibitors are not allowed in PD0053. However, if they are taken, a 'hypothetical' strategy will be used in all analyses for these medications and post-ICE data will be set to missing. Taking MAO-B is considered a protocol deviation which is also considered an ICE, and therefore also covered in [Section 1.2.3](#).

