### **6.5.3        Rescue medication**

Investigators will be encouraged to carefully document all changes and dose adaptations, particularly when considering ST initiation which should always consider the individual participant needs and standard of care recommendations. Guidance on the initiation of rescue medication will be provided in a separate manual.

The study site will supply rescue medication that will be obtained locally.

Levodopa is determined as first choice for participants who are determined to require ST. Other ST options are only permitted in exceptional cases, where levodopa has an unsatisfactory effect, where contraindications against levodopa are identified by the Investigator, or where an alternative ST drug is medically indicated for any other reason. Monoamine Oxidase Type B inhibitors will not be allowed.

The date and time of onset of rescue medication administration, as well as the name and dosage regimen of the rescue medication, must be recorded in the eCRF. Any dose adjustments also need to be recorded.

For all scheduled visits, study participants that start to receive ST over the study observation period will be asked to refrain from taking ST for at least 12 hours before the clinic visit and to bring the medication to the site. A 12-hour washout is considered sufficient to achieve a practically defined off-state for the range of STs specified in this section and has proven tolerable in clinical practice (Bloem et al, 2019). All tests which are expected to be sensitive to the effects of ST will take place throughout the first part of the study visit to allow resuming

dosing of ST at the earliest possible point. If a participant does not comply with the 12-hour ST washout prior to any visit, the data from that particular visit will be censored.

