Population summary measure	For Part I-III sum score: Difference in slope of progression at 12 months (primary) and difference in mean at 12	For Part III subscale: Difference in RMET (time to confirmed first 5-point increase or ST	For Part I-III sum score: Difference in mean at 12 and 18 months (supplementary)

Table 1–2: Overview of handling strategies for ICEs, ICE-like protocol deviations and study termination or loss to follow-up for MDS-UPDRS estimands

	
and 18 months (key secondary and supplementary)^a
 
For Part III subscale: Difference in slope of progression at 12 months (key secondary)
 
For Part III subscale and Part III ePD subscore^a: Difference in mean at 12 and 18 months (key secondary)
 
For Part I/II subscale: Difference in mean at 12 and 18 months (secondary)
	
initiation) within 18 months (key secondary)
 
For Part II subscale: Difference in RMET (time to confirmed first 3-point increase or ST initiation) within 18 months (supplementary)
	
For Part I/II/III subscales: Difference in mean at 12 and 18 months (supplementary)

ICE & ICE-like protocol deviations			
ST initiation (Non-MAO-B Inhibitors) ^c	Hypothetical (set to missing & impute all post ICE visit data – MAR/ML)	Composite (ICE is part of the endpoint)	Treatment policy (Include post-ICE data)
ST initiation (MAO-B Inhibitor) ^c	Hypothetical (set to missing & impute all post ICE visit data – MAR/ML)	Composite (ICE is part of the endpoint)	Treatment policy (Include post-ICE data)
Treatment discontinuation (Lack of efficacy or AE)	Treatment policy (Include post-ICE data)	id	id
Treatment discontinuation (Other causes)	Treatment policy (Include post-ICE data)	id	id
Important ICE-like protocol deviations			
with long-term impact ^d	Hypothetical (set to missing & impute all post ICE visit data – MAR/ML)	Hypothetical (set to missing & treat as right-censored (non-event) at time of initial IPD)	id
With short-term impact ^d	Hypothetical (set to missing & impute single post-ICE visit data – MAR/ML)	Hypothetical (ignore)	id

Table 1–2: Overview of handling strategies for ICEs, ICE-like protocol deviations and study termination or loss to follow-up for MDS-UPDRS estimands

Death or serious injury (all causes)	Actual missing: impute all post ICE visit data – MAR/ML	Actual missing: treat as right-censored (non-event) at time of termination	id

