Table 1–3: Overview of handling strategies for ICEs, ICE-like protocol deviations and study termination or loss to follow-up for other estimands

With long-term impact ^c	Hypothetical (set to missing & impute all post ICE visit data – MAR/ML)	Hypothetical (set to missing & treat as right-censored (non-event) at time of initial IPD)	id
With short-term impact ^c	Hypothetical (set to missing & impute single post-ICE visit data – MAR/ML)	Hypothetical (ignore)	Treatment policy (Include post-ICE data)
Death or serious injury (all causes)	Hypothetical (set to missing & impute all post ICE visit data – MAR/ML)	Actual missing: treat as right-censored (non-event) at time of termination	id
COVID-19 related ICEs without Treatment discontinuation or study termination	Treatment policy (Include post-ICE data)	id	id
Missed visits, study termination and loss to follow-up			
Missed visit(s) (intermittent) ^e	Actual missing: impute visit data – MAR/ML	Actual missing: ignore	Actual missing: impute visit data – MAR/ML
Study termination: Treatment-related	Actual missing: impute all post termination visit data – MAR/ML	Actual missing: Imputed as non-response (event) to randomized treatment under MNAR ^d	Actual missing: impute all post termination visit data – MAR/ML
Study termination and loss to follow-up: Other/unknown cause	Actual missing: impute all post termination visit data – MAR/ML	Actual missing: will be treated as right-censored (non-event) at the time of termination	Actual missing: impute all post termination visit data – MAR/ML

AE=Adverse Event; COVID-19 = Coronavirus Disease-2019; DaT-SPECT=Dopamine Transporter Imaging with Single Photon Emission Computerized Tomography; ICE=Intercurrent Event; id = idem, “the same” across rows; MAR = Missing at Random; ML = Maximum Likelihood; MNAR = Missing Not at Random; MoCA=Montreal Cognitive Assessment; RMET=Restricted Mean Event Time; SBR=Specific Binding Ratio; ST=Symptomatic Treatment.

^bSee [Section 5.3.3.3](#) for how to determine which type of ST a medication is.

^cThe category that each protocol deviation falls into will be defined outside of the SAP, in the protocol deviation specifications or a separate document. Only important protocol deviations can be ICEs, but not all important protocol deviations will be defined as ICEs.

^dTreatment-related study-termination is classed as an event (ie, non-response) in the RMET analysis for ST initiation.

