5.3.2.4.1 Time to ST Initiation

Definitions of endpoints

The participant-level endpoint will be time from Baseline to start of ST or last censored time observation within the 18-month period.

Main analytical approach

Full details on the ICE handling for this estimand can be found in [Section 1.2](#). The main ICEs for this estimand will be study termination and loss to follow up (see details in [Table 1–3](#)).

The population level summary will be the difference in target population restricted mean event time (RMET) up to the last observed event time within the 18-month period between:

- UCB0599 high dose (360mg/day) and placebo
- UCB0599 low dose (180mg/day) and placebo.

In this study, the RMET can be interpreted as the average time until ST initiation within the study period. This summary was chosen as it has been shown to be robust when the proportional hazards assumption does not hold, can be estimated even under heavy censoring, and has an easy clinical interpretation (Royston and Parmar, 2013).

As the main analysis for time to ST initiation, RMET from Baseline to the last observed event time will be estimated. This analysis will use the same modelling approach as described for the MDS-UPDRS Part III subscale time to worsening analysis (see [Section 5.3.2.1.5](#) for further details). By default, this approach makes the assumption that the right-censoring mechanism is homogeneous among all participants, which may not be a valid assumption in this study; censoring in the context of this analysis will come from study termination and it is possible that termination may be higher or lower in the UCB0599 arms compared to placebo. To counter this potential bias, we will obtain treatment group-specific weights by applying the KM estimation method separately to each group (ie, using treatment group as a stratification variable in the model). A summary table presenting the adjusted difference in RMET of ST intake between each UCB0599 treatment group and placebo and the corresponding 95% CIs will be produced, this summary will also include the model estimates of adjusted RMET for each treatment group.

Sensitivity analyses

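### For a first symptomatic treatment (ST) that is a MAO-B inhibitor, the SAP's ST rules score an event while its protocol-deviation rules can censor a non-event, and no precedence is stated

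*SAP*

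**What the plan says.** **Status of the drug class.** Protocol Section 6.5.3 says of rescue: "Monoamine Oxidase Type B inhibitors will not be allowed". Inclusion criterion 7a nevertheless lists the class among medications for motor symptoms of PD, and SAP Section 1.2.1 sets rules in case the drugs are taken.

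**ST rows.** SAP Table 1-2 has a separate row, "ST initiation (MAO-B Inhibitor". It is hypothetical in the absence-of-ST column, "Composite (ICE is part of the endpoint" in the time-to-worsening column, and treatment policy in the regardless-of-ST column. The MAO-B row of Table 1-3 is hypothetical for DaT-SPECT, NA for ST intake and treatment policy for MoCA.

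**Section 1.2.1, DaT-SPECT subsection.** For MAO-B inhibitors a hypothetical "strategy will be used in all analyses for these medications and post-ICE data will be set to missing". The next sentence reads "Taking MAO-B is considered a protocol deviation which is also considered an ICE, and therefore also covered in" Section 1.2.3.

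**Deviation rows.** For a deviation with long-term impact, the event-endpoint columns of Tables 1-2 and 1-3 say "Hypothetical (set to missing & treat as right-censored (non-event) at time of initial IPD". For short-term impact they say to ignore it. Footnotes to both tables place the long-term or short-term grading in another document.

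**Endpoint definitions.** In Section 5.3.2.4.1, "The participant-level endpoint will be time from Baseline to start of ST or last censored time observation within the 18-month period". Section 5.3.2.4.2 uses a yes/no variable for having started ST. Neither excludes a drug class.

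**Section 1.2.1, MDS-UPDRS subsection.** "Only Levodopa and Dopamine-agonist STs will be considered as having an impact on MDS-UPDRS". The same sentence sends other ST types to Table 1-2 and cites Section 5.3.3.3 for classification.

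**The concern.** Take one participant whose first motor ST is a MAO-B inhibitor. Two sets of table rows apply to that start, and for the event endpoints they give opposite answers: event, or censored non-event. A programmer must choose, and the SAP does not say how.

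Section 1.2.3 treats important deviations as uninformative. That cannot hold here. For time to ST initiation the deviation is the event, and for time to worsening it is a component of the composite. Censoring at that moment removes an outcome and lengthens the arm's apparent event-free time. The endpoints at stake are Part III time to worsening (key secondary), Part II time to worsening (supplementary), time to ST initiation and ST intake.

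**Working it through.** The plan states no figure on this point, so there is none to reproduce. The check sets the rules side by side and then sizes one recoded participant.

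**Rules for one MAO-B start**

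| Analysis | ST row or endpoint definition | Long-term deviation row |
|---|---|---|
| Part III and Part II time to worsening | event | right-censored non-event |
| Time to ST initiation, ST intake | event by definition; ST rows of Table 1-3 are NA | right-censored non-event |
| MDS-UPDRS regardless of ST | keep post-start data | hypothetical (carried across as the same) |
| MoCA | keep post-start data | hypothetical (carried across as the same) |
| Primary slope | remove post-start data | remove post-start data |
| DaT-SPECT | remove post-start data | remove post-start data |

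Use of prohibited medication is a named category of important deviation in SAP Section 5.1.2.2, so the deviation rows are a live route. If the deviation is graded short-term, the event endpoints ignore it, but the SAP does not say whether the ST start still counts. For ST intake, which is binary, right-censoring does not say whether the participant is missing or counted as not on ST.

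**Size per recoded start (illustration)**

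Inputs: 150 randomised per arm (Protocol Section 9.7.1); ST initiation by month 12 of 20% (planning value) or 58% (PPMI cohort), both from SAP Section 3.2. Assumptions: exponential time to ST, otherwise complete follow-up to month 18, and Kaplan-Meier redistribution of a censored participant to later times.

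- Hazard: h = −ln(1 − p)/12. For p = 0.20, h = 0.0186 per month; for p = 0.58, h = 0.0723.
- RMET to 18 months: (1 − exp(−18h))/h = 15.30 and 10.07 months.
- Shift in the arm's RMET when a start at month t is censored instead of counted: [(1 − exp(−h(18 − t)))/h]/150.

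| Start month | p = 0.20 | p = 0.58 |
|---|---|---|
| 3 | 13.09/150 = 0.087 | 9.16/150 = 0.061 |
| 6 | 10.76/150 = 0.072 | 8.02/150 = 0.053 |
| 9 | 8.29/150 = 0.055 | 6.62/150 = 0.044 |
| 12 | 5.68/150 = 0.038 | 4.87/150 = 0.032 |

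Five such starts at month 6 in one arm would shift its RMET by 5 × 10.76/150 = 0.36 month or 5 × 8.02/150 = 0.27 month.

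For comparison, the standard error of an RMET difference is approximately SD × √(2/150), where SD² = 2[1 − exp(−18h)(1 + 18h)]/h² − RMET². This gives 0.59 and 0.74 month.

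These figures are for time to ST initiation. The time-to-worsening composite has at least as high a hazard, so its shift per start would be no larger.

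**The case against.** The strongest reply has four parts.

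1. *The all-analyses sentence is about DaT-SPECT only.* It closes the DaT-SPECT subsection and matches the DaT-SPECT cell of Table 1-3. A reader might infer that it overrides the MDS-UPDRS and MoCA cells; its position does not support that. This part stands. It does not remove the conflict, which comes from the next sentence (the start is also a deviation) together with the deviation rows.

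2. *MAO-B starts are not treated as having no effect.* A reader might infer this from the sentence limiting MDS-UPDRS impact to levodopa and dopamine agonists. That sentence sends other types to Table 1-2, which has a MAO-B row. This stands too: the stated rationale disagrees with the row, but it is not a further operational rule.

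3. *Censoring is conditional, and NA is not a gap.* The censoring rule applies only if the deviation is graded long-term, in a document not available here. NA is also natural where ST is itself the response, and the endpoint definitions count any start. Both are fair. But NA leaves the deviation row as the only substantive table rule a MAO-B start meets in that column, and nothing says the endpoint definition prevails. Section 5.3.2.4 adds doubt by pointing to Protocol Section 6.5.3 for which STs are permitted.

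4. *Few participants are affected.* The class is prohibited and levodopa is first choice. This stands and limits the size. A reader might infer a material bias by assuming a sizeable or unequal MAO-B share between arms; the documents give no share to support that.

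**Conclusion.** The conflict is real for the event endpoints. One MAO-B start is an event under the ST row or the endpoint definition, and a censored non-event under the long-term deviation row, with no precedence and with the grading left outside the SAP. If the deviation row were applied, censoring would be informative. The regardless-of-ST MDS-UPDRS and MoCA analyses have a parallel clash between treatment policy and the deviation rows, and with the all-analyses sentence only if that is read literally.

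It would be wrong to conclude that the primary result can be coded two ways. The MAO-B row, the long-term deviation row and the literal Section 1.2.1 sentence all remove post-start data from the slope analysis. A short-term grading would matter there only if it displaced the ST row.

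The size is modest: about 0.03 to 0.09 month of RMET per recoded start at months 3 to 12, under the assumptions above. Five month-6 starts in one arm would amount to 0.36/0.59 = 0.6 or 0.27/0.74 = 0.4 of a standard error. The actual number of MAO-B starts is unknown and should be small. The point is worth fixing because it leaves an avoidable coding choice on a key secondary endpoint and on the ST endpoints.

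**What to change.** In SAP Section 1.2.1:

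- Limit the all-analyses sentence on MAO-B inhibitors to the DaT-SPECT analyses.
- State that, for a MAO-B start, the ST-initiation rows of Tables 1-2 and 1-3 take precedence over the protocol-deviation rows.
- State that a MAO-B start counts as an event in time to worsening, time to ST initiation and ST intake. This is needed as well as the precedence rule, because the ST cells for ST intake in Table 1-3 read NA.
- Reconcile the sentence on levodopa and dopamine agonists with the MAO-B row of Table 1-2. It need not be deleted; deletion would also change the stated rationale for other ST classes.
- Correct the cross-reference to Section 5.3.3.3, which holds no classification of ST types and leaves conversion factors to the ADaM reviewer's guide.

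The cost is SAP wording, one derivation rule and a few recoded records, settled before unblinding. The change concerns analysis coding only and takes no position on which rescue drugs should be used.

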1.2.2 Treatment discontinuation and treatment-related ICE-like protocol deviations

Participant-led or Investigator-led treatment discontinuation may be related to assigned investigational treatment (due to lack of efficacy / AEs) or unrelated.

Note that some of the participants who discontinue assigned investigational treatment due to lack of efficacy (whether on placebo or UCB0599) may want to start taking ST and therefore their data will be handled as such.

Treatment discontinuation will not be considered to impact the definition of the intervention effect of interest, and the post-ICE data will be included in the analyses ('Treatment policy' strategy).

Minor treatment-related protocol deviations such as IMP treatment non-compliance (missing a dose or taking a dose at a different time of the day) or minor drug administration error will not be considered to impact the definition of the intervention effect of interest and the post-ICE data will be included in the analyses ('Treatment policy' strategy).

1.2.3 Other ICE-like protocol deviations

Some protocol deviations can be defined as ICEs. The protocol deviations specification document will clearly define the protocol deviations that are ICEs and the type of impact they will have.

For important protocol deviations considered to impact the effect of interest on the long-term, the deviation will be considered uninformative with respect to the treatment of interest and the post-ICE data will be removed from the analyses for all following visits and the post ICE missing data will be imputed ("Hypothetical" handling strategy) assuming (MAR) and using ML imputation.

For important protocol deviations considered to only impact the effect of interest in the short-term, e.g. a single visit, the deviation will be considered uninformative with respect to the treatment of interest and data for the impacted visit(s) will be removed from the impacted analyses and the post ICE missing data will be imputed ("Hypothetical" handling strategy) assuming (MAR) and using ML imputation.

Further details on protocol deviations are given in [Section 5.1.2.2](#).

1.2.4 Death or serious injury

Local injuries eg, to arms/hands or legs/feet for MDS-UPDRS and to head for DaT-SPECT, or systemic acute conditions such as a stroke or an accident-related coma may prevent the taking of measurements. Treatment-related death or death due to other causes (including COVID-19) may occur during the study. Death due to PD is unlikely, as participants have been selected in the early stage of PD, although an accident may be the consequence of PD symptoms.

Both PD-related and non PD-related serious injury or death will be considered uninformative with respect to the definition of the effect of the intervention of interest, and the post-ICE data will be set to missing in the analyses ('Hypothetical' strategy). In practice, these events will be identified as serious adverse events that result in persistent or significant disability/incapacity or death.

